3.5 RECRUITMENT

3.5.1 Participant identification

Potential participants will be identified by the clinical co-investigators, as named on page 8 of this document, at LHCH. Identification of potential participants will be based on ejection fraction measurements as determined by the results of a retrospective 3D echocardiogram. Patients who have been referred to LHCH cardio-oncology clinic with suspected doxorubicin-induced cardiotoxicity will have received a 3D echocardiogram and blood-based biomarker test at the time of their outpatient appointment and either been diagnosed with cardiotoxicity or discharged back to their referring oncologist with negative test results. LHCH will approach those who fit the inclusion criteria from this selection of patients to be involved in the study. Once eligible cardiotoxicity participants have been identified at LHCH, non-cardiotoxicity subjects will be identified based on their retrospective test

Version 2.24. Date: 1547/095/2022; IRAS:

Page 22 of 44

results and matched to the cardiotoxicity subjects on tumour type, age, and treatment regime (including dosage and time frame). Non-cardiotoxicity subjects will be approached to take part as a control cohort by one of the named clinical co-investigators.

Eligible participants will be given basic information about the study by the co-investigator either during their outpatient appointment, over the phone, or by an invitation letter sent in the post. Patients who are interested in finding out more about the study will be given a Patient Information Sheet and the option to leave their telephone number for the clinical team to make contact, or to contact the clinical team themselves using the contact information given on the PIS.

Participants will not be recruited through Patient Identification Centres, disease registers, or through media advertising such as posters, leaflets, adverts, or websites. Participants will not receive any payment for participation in this study.

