3.6 SAMPLING

3.6.1 Size of sample

The maximum sample size for this pilot study at this stage will be 12 participants in total across all experimental groups (Figure 1). When selecting a sample size for this study we considered several factors including the nature of the study (i.e. a pilot study) and the financial feasibility of achieving our research aims at this stage. As this is a pilot study, we want to generate preliminary data that can support further funding applications that build on scientific evidence and eventually allow for larger sample sizes whilst still working realistically within the constraints of the study. Our approach is therefore to focus our efforts on obtaining a carefully planned smaller sample size which adequately represents significant aspects of the wider study population. This sample size is large enough to sufficiently address the primary research aims at the current stage and will provide valuable preliminary data to plan larger subsequent studies which will further address the overarching research questions.

Version 2.21. Date: 1517/095/2022; IRAS:

Page 23 of 44

Formatted: Indent: Left: 0.35 cm

[figure not shown]

Figure 1. Cancer patients with early-onset chronic cardiotoxicity and late-onset chronic cardiotoxicity will be recruited. Non-cardiotoxic patients will be matched to the cardiotoxic patients on tumour type, treatment regime and approximate age. For late-onset chronic cardiotoxic patients, noncardiotoxic patients will be recruited who have previously received the same treatment regime and not developed cardiotoxicity at the same point.

Version 2.21. Date: 1517/095/2022; IRAS:

Page 24 of 44

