6.2.2.7 Mass Spectrometry (MS)

Version 2.24. Date: 1547/095/2022; IRAS:

Page **31** of **44**

To generate quantitative data on the whole proteome of doxorubicin-treated cardiomyocytes, cardiomyocytes from all experimental groups will be subjected to iTRAQ-based MS. To determine whether protein expression is similar between cardiotoxicity and non-cardiotoxicity samples, the data will be subjected to principal component analysis to analyse the variance across the sample sets and identify whether there is a distinction between them based on protein expression. A two-tailed *t* test will be carried out using the R computational environment to determine the statistical significance of differences in protein expression between cardiotoxicity and non-cardiotoxicity samples

To validate the iTRAQ-MS data, we will use Western blot analysis to verify the differential protein expression of a select number of identified proteins. The identity of the target proteins will be confirmed by comparison to a molecular weight marker (for size) and a positive control if possible (for size and signal). A loading control will be used to allow us to normalise the data and compare the expression levels between the target proteins. The data produced will be interpreted using imaging software, such as ImageJ, and a semi-quantitative comparison will be made of the signals generated between protein bands.

Following validation, proteins which are found to have a statistically significant higher or lower level of expression by MS in the control samples will be explored further using computational enrichment analysis to identify functional pathways involved in cardiotoxicity.

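### The proteomics plan passes a list of t-test-significant proteins, with no stated error control, to an unnamed enrichment analysis; run as a standard over-representation test, this can declare co-regulated pathways enriched when cases and controls do not differ

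*Protocol*

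**What the plan says.** Protocol section 6.2.2.7 sets out a chain of steps.

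1. Mass spectrometry is used "To generate quantitative data on the whole proteome of doxorubicin-treated cardiomyocytes".
2. The two groups are then compared: "A two-tailed *t* test will be carried out using the R computational environment to determine the statistical significance of differences in protein expression". No threshold and no adjustment over proteins is given.
3. For validation, "we will use Western blot analysis to verify the differential protein expression of a select number of identified proteins".
4. The input to the last step is "proteins which are found to have a statistically significant higher or lower level of expression by MS in the control samples". These "will be explored further using computational enrichment analysis to identify functional pathways involved in cardiotoxicity".

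The section names no enrichment statistic, background set, null hypothesis or resampling unit.

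On size, section 3.6.1 states: "The maximum sample size for this pilot study at this stage will be 12 participants in total across all experimental groups". The split between groups cannot be read from the text, because Figure 1 is not shown. Section 3.5.1 matches controls to cases on tumour type, age and treatment regime. Section 3.6.1 also gives the purpose: "As this is a pilot study, we want to generate preliminary data that can support further funding applications".

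**The concern.** The conclusion in step 4 is about patients: which pathways differ between those who did and did not develop cardiotoxicity. The material handed to that step is a thresholded list of proteins. The ordinary analysis of such a list asks whether it holds more members of a pathway than the same number of proteins drawn at random from a background. The sampling unit is then the protein, and proteins are treated as exchangeable and independent.

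Proteins in one pathway tend to rise and fall together between donors. With about six donors a side, a chance imbalance in whatever drives the pathway moves many members across the threshold together. The over-representation test reads the cluster as evidence. Adjusting the pathway p-values for the number of pathways does not help, because each p-value is already computed against the wrong reference.

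At stake is the direction of later work. The pilot is meant to support funding applications, and section 3.3 lists as a secondary outcome a biological process that is present in cases and absent in controls. A false pathway would steer both.

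**Working it through.** The Protocol gives no alpha, power or error rate for this step, so there is no figure of its own to reproduce. The check is a simulation with no case-control difference.

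**Inputs from the Protocol:** at most 12 donors (3.6.1); a two-tailed t test per protein, significant proteins passed to enrichment (6.2.2.7).

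**Assumed, not in the Protocol:** a 6 v 6 split, the unpaired form of the t test, the number of proteins, the number and size of pathways, a common within-pathway correlation rho, and a list formed at unadjusted p<0.05.

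**Enrichment test.** With M proteins, S of them listed, and k listed members in a pathway of size m, the p-value is P(X ≥ k), X hypergeometric(M, m, S). Benjamini-Hochberg at 5% is applied across pathways.

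- Setting A: M = 3,000, 60 pathways of 50 (60 × 50 = 3,000, so every protein is in a pathway). Expected list 0.05 × 3,000 = 150; expected listed members per pathway 50 × 150/3,000 = 2.5.
- Setting B: M = 6,000, 100 pathways of 30 (half of the proteins are in pathways). Expected list 0.05 × 6,000 = 300; expected listed members per pathway 30 × 300/6,000 = 1.5.

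**Why correlation matters.** The variance of a pathway's average group difference is 1 + (m − 1)rho times its value under independence. At rho = 0.2 this is 1 + 49 × 0.2 = 10.8 in setting A and 1 + 29 × 0.2 = 6.8 in setting B. The hypergeometric reference has no term for it.

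**Chance of at least one pathway declared, no true difference, 6 v 6:**

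| rho | Setting A, two sets of runs | Setting B, 600 studies |
|---|---|---|
| 0 | 1%, 2% | 3% |
| 0.1 | 14%, 15% | 10% |
| 0.2 | 61%, 65% | 48% |
| 0.3 | 87%, 91% | 84% |

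A further repeat of setting A (300 studies) gave 1%, 21%, 59% and 92%. At rho = 0.05 the rates are 5% (A) and 3% (B). In setting B at rho = 0.2, other splits give 26% (3 v 3) and 44% (4 v 8).

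**Is the reference distribution the cause?** In setting B the same list and the same pathway counts were referred to all 924 relabellings of donors, using the maximum over pathways (120 studies per rho):

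| rho | Hypergeometric reference | Donor-label reference |
|---|---|---|
| 0 | 3.3% | 4.2% |
| 0.2 | 45% | 5.0% |

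The Monte Carlo standard error at 5% is √(0.05 × 0.95/120) = 2 points. In setting A a correlation-adjusted competitive set test on all proteins gave 2-4%. A rotation set test was not simulated.

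**What if the list is FDR-controlled?** In setting B with the list formed at 5% FDR, the list was non-empty in about 4-6% of null studies, and a pathway was declared in at most 0.2% at every rho. With real differences scattered evenly over pathways, false pathways occurred in 0-0.3% up to rho = 0.3 and about 5% at rho = 0.5.

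**Resolution of label permutation.** For a two-sided statistic the smallest p is 2/C(12,6) = 2/924 = 0.0022 unpaired. If labels may be swapped only within six matched pairs, it is 2/2⁶ = 2/64 = 0.031.

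**The case against.** The strongest objection is that the faulty null is not in the document. A reader might infer from section 6.2.2.7 that the plan adopts a test treating proteins as independent. It does not say so, and an analysis plan that is not at hand might specify something better. That stands: the point is conditional on the ordinary over-representation test being used. The Protocol does nonetheless fix the list input and the conclusion to be drawn, and the ordinary test is the natural way to join them.

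A reader might also infer that a list as input forces this null, so that list enrichment has to be abandoned. It does not: donor-label permutation of the list-and-count procedure held about 5%.

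An FDR-controlled list removes the excess when nothing differs. That also stands, so under the complete null the inflation depends on forming the list without error control. Section 6.2.2.7 states none. With so few donors a controlled list would usually be empty under the null, which makes the unadjusted list the tempting one.

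The words about validation could be read as restricting enrichment to blot-verified proteins. But only a select number are blotted, the comparison is semi-quantitative, and the enrichment input is defined by significance on mass spectrometry. Re-measuring the same donors would not expose a chance imbalance between them.

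Finally, this is a pilot. Its primary outcome is generating cardiomyocytes, and proteomic profiling is one of five Aim 2 objectives. A reader might take the pathway result to be the study's only route to a mechanism; section 2.1.2 does not support that. This limits the weight of the point but does not remove it.

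**Conclusion.** The point holds in conditional form. If the chain in section 6.2.2.7 is followed with an unadjusted p<0.05 list and a standard over-representation test, co-regulated pathways can be declared enriched with no case-control difference, despite correction across pathways. The risk is negligible at correlations of 0.05 or less, noticeable at 0.1, around one in two or more at 0.2, and high at 0.3.

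These sizes rest on the assumed split, protein count, pathway structure and common correlation, none of which the Protocol gives. It would be too strong to say that false pathways are certain, or likely whatever is done: that needs both an uncontrolled list and moderate correlation. The matter deserves correction before analysis because the stated inference is about patients and the pathways are meant to guide larger studies.

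**What to change.** Amend section 6.2.2.7 as follows.

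1. Base pathway p-values on all quantified proteins, with the donor as the unit and allowance for correlation between proteins. Options are a correlation-adjusted competitive set test, a rotation set test, or donor-label permutation of the whole list-and-enrichment procedure. State which, and how the matching enters.
2. Adjust across pathways for the false discovery rate.
3. State the FDR control applied to any protein list that is used.
4. Label list-based enrichment descriptive, and the pathways hypothesis-generating.

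The cost is wording and standard code in the R environment already planned; no new data are needed. Fewer pathways will be called, with less favourable p-values.

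Permutation is coarse here. Benjamini-Hochberg at 5% over 60 pathways needs at least 0.0022 × 60/0.05 = 2.6, so three pathways, at the unpaired minimum before any is declared. Within six pairs it needs 0.03125 × 60/0.05 = 37.5, so 38. If permutation is chosen, the maximum over pathways avoids this particular obstacle but controls the family-wise error rate, so the plan should then say that it replaces the FDR adjustment.

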6.2.2.8 Electrophysiology

We will use standard electrophysiological and fluorescence imaging techniques to characterise the electrical activity and calcium homeostasis in iPSC and cardiomyocyte cell lines. Patch clamp recordings will be made from single cells using microelectrodes formed from thick walled borosilicate glass filled with an electrolyte solution connected to an industry standard amplifier (Axopatch 200B), digitised (Digidata 1440) and recorded using specialised electrophysiological recording software (pCLAMP10.7). It is anticipated that we will measure ionic currents, in particular K⁺ and Ca²⁺ along with the cardiac action potential to investigate morphological and pathophysiological changes in the whole cell electrical signalling that may correlate with disease states. In particular, current amplitude will be measured using voltage-protocol appropriate to the current under investigation. Action potential amplitude and duration will be measured as these are common markers of electrical dysregulation.

In order to study the responses to electrical signalling, we will use state-of-the-art fluorescence measurements to measure intracellular Ca²⁺ changes correlating to each contractile cycle (using fluo-3, fluo-4 or Fura-2), along with intracellular ATP (using MgGreen), mitochondrial function (using TMRE/TMRM) and membrane potential (using Di-4-ANNEPS or Di-8-ANNPES) across the syncytium of cells using cell permeant fluorescent markers. Fluorescence will be excited using a PTI monochromator attached to a Nikon TiU microscope with fluorescence signals detected using a Andor Zyla camera controlled by Winfluor4.5 software. In all cases, daily control data sets will be gathered along with any test data sets. Calcium fluorescence signals from either spontaneous action potentials or from electric field stimulation for pacing of cells, will be analysed for peak amplitude, transient duration and measurement of the area under the curve to assess changes. ATP and mitochondrial membrane potential will be measured for responsiveness to simulated ischaemia, where cells exposed to toxic conditions generally show an increased rate of mitochondrial depolarisation and rapid ATP depletion. Finally, membrane potential indicators will be used to measure the spread of excitation through the syncytium. Measurements of the rate of depolarisation and the delay across the syncytium will be

Version 2.24. Date: 1547/095/2022; IRAS:

Page 32 of 44

assessed. These protocols are well established in the group, and standard data analysis protocols and statistical analysis are established and are used in peer-reviewed published manuscripts.

All raw electrophysiological recordings will be available in pCLAMP format (.abf files), whilst all imaging data will be stored as time stamped image files (.tif) or image stacks readable in ImageJ.

76 ETHICAL & REGULATORY CONSIDERATIONS

7.1 ETHICS APPROVAL AND OTHER REGULATORY REVIEWS AND REPORTS

The CI will obtain approval from the appropriate Research Ethics Committee and Health Research Authority (HRA) approval for the study protocol, PIS, informed consent forms and other relevant documents with respect to the scientific content and compliance with the tenets of the Declaration of Helsinki prior to commencing recruitment. The study will be submitted to each proposed researchsite for Confirmation of Capacity and Capability. The study will be conducted in accordance with the recommendations for physicians involved in research on human subjects adopted by the 18th World Medical Assembly, Helsinki 1964 and later revisions

Substantial amendments that require review by NHS REC will not be implemented until that review is in place. All correspondence with the REC will be retained.

The CI will produce the annual reports as required and notify the REC of the end of the study. If an annual report is required for this study, an annual progress report will be submitted to the REC within 30 days of the anniversary date on which the favourable opinion was given, and annually until the study is declared ended. If the study is ended prematurely, the CI will notify the REC, including the reasons for the premature termination. Within one year after the end of the study, the CI will submit a final report with the results, including any publications/abstracts, to the REC.

7.1.1 Regulatory Review & Compliance

Before any participating site starts to enrol subjects into the study, the CI will ensure that appropriate approvals from participating organisations are in place.

For any amendment to the study the CI, in agreement with the Sponsor, will submit information to the appropriate body for them to issue approval for the amendment. The CI will work with participating sites to put the necessary arrangements in place to implement the amendment.

7.1.2 Amendments

Any substantial changes to the protocol which may impact on the conduct of the study, potential benefit of the patient or may affect patient safety, including changes of study objectives, study design, patient population, sample sizes, study procedures, or significant administrative aspects will require a formal amendment to the protocol. Such amendments will be agreed upon by the CI and the grant applicants and approved by the appropriate REC prior to implementation.

Administrative changes (minor corrections and/or clarifications that have no effect on the way the study is to be conducted) to the study protocol will be agreed upon by the CI and the grant applicants

Version 2.21. Date: 1517/095/2022; IRAS:

Page 33 of 44

and will be documented in a memorandum. The REC may be notified of administrative changes at the discretion of the CI.

7.2 CONSENT

To gain informed consent, a member of the clinical team will discuss with the potential participant, or his/her representative, the nature and objectives of the study as well as the potential risks and benefits associated with participating. Potential participants who are interested in finding out more about the study will be provided with a REC approved written (English) PIS whose content will be written in a way which is easy to understand and will include details relating to: the purpose of the study, the voluntary nature of participating, data collection and use of data, risks and benefits of participating, storage and reuse of samples, necessary contact information for both the clinical and research teams, withdrawal procedures, and how to file a complaint.

Potential participants will be given the opportunity to ask the clinical staff any questions and [if they wish] to discuss their interest in participating with others before choosing to take part. Capacity to consent will be assessed by the clinical team (i.e. the consenting clinician/research nurse). A member of the clinical team will assess a potential participant's capacity to consent through their understanding of the purpose of the research and its objectives, what the research involves, and what the potential risks and benefits of participating are. Potential participants will be asked whether they have discussed their decision to participate with anyone else to establish whether they have been coerced to participate. Individuals deemed to lack the capacity to consent or deemed to have been coerced to consent will not be enrolled on the study. Patients will be reassured that they can withdraw from the study at any time without the decision impacting on their clinical care.

Any samples collected prior to the point of withdrawal from the study will only be used with prior consent. All participants will be enrolled onto the study by signing a consent form. A hard copy of the consent form will be stored by both the participating hospital site at which the participant is enrolled and by the research team at the University of Liverpool. A copy will also be given to the participant. The consent form will include the following statements:

- That they have read and understood the information sheet
- Participation is voluntary and they can change their mind at any time
- That they understand that their care will not be affected by the decision to participate

• If any concerns about the participants ongoing health arise during the interview, we are obliged to disclose these to their GP

The protocol for re-approaching patients and consenting them is outlined in section 3.5.1. Patient recruitment,

7.3 DATA PROTECTION AND PATIENT CONFIDENTIALITY

The CI will preserve the confidentiality of participants taking part in the study and will abide by the EU General Data Protection Regulation 2016 and Data Protection Act 2018. All co-investigators and studysite staff will comply with the requirements of the Data Protection Act 2018 with regards to the collection, storage, processing, and disclosure of personal information and will uphold the core principles of the Act.

Version 2.24. Date: 1517/095/2022; IRAS:

Page 34 of 44

-[Formatted: Font: 11 pt
-(Formatted: Indent: Left: 0.35 cm
1	Formatted: Font: 11 pt

Once they have entered the study and signed the consent form, participants will be assigned a unique study number by a research nurse. Their clinical and demographic details, as judged

Version 2.24. Date: 1547/095/2022; IRAS:

Page **35** of **44**

relevant to the study by the clinical team and excluding any primary identifiers, will be entered into a secure database accessible to both the clinical team and the research team. All blood tubes used for sampling of a participant will be labelled with the participant's study number and the research team will be able to use this number to gain relevant information from the database for data analysis purposes, whilst also maintaining patient anonymity. The key that links a participant's study number to their primary identifiers (name, date of birth and NHS number) and the details of the key will be retained in secure facilities, separate from the data, and in accordance with data protection and information governance policies at the University of Liverpool and LHCH. Access to the key will be limited to the minimum number of individuals necessary for quality control and audit purposes.

All study-related information will be stored securely at the study site and all participant information will be stored in locked filing cabinets in areas with limited access and/or on password-protected computers. Sensitive personal data (e.g. sexual orientation, health records, religion, ethnicity, biometric data, personal identifiers etc) will be handled in such a way that no individual can be identified from the data without a coded ID which allows the data to be re-identified. This means that direct and indirect identifiers will be obscured or removed, and study records identified by the coded ID kept separately in a secure manner from study records containing any personal identifiers. Whilst it is acknowledged that pseudoanonymised data such as this is still considered personal data, this method is actively encouraged under GDPR security measures.

All clinical test results will be kept strictly confidential and clinical procedures will be conducted in a private room. Participants' study information will not be released outside of the study without the written permission of the participant.

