6.2 DATA ANALYSIS

6.2.1 Clinical data analysis

Patient demographics and clinical test results will be recorded by the clinical team for the purposes of the study and will be accessible to the clinical team only. A list of the relevant clinical data that will be collected can be found in Appendix 13.1.3. Access to patient records to identify potential participants and check whether they meet the relevant inclusion criteria will be restricted to the patient's existing clinical care team only - which in all cases will be one of the three named co-investigators on page 8 of this document or, on occasion and at their discretion, their appointed research nurse.

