6.2.2 Experimental data analysis

All experimental methods carried out during this study will be conducted at the University of Liverpool by the study's designated research assistant. All experimental data generated will be processed and analysed using University equipment and any appropriate commercially available software as deemed necessary by the study's PI. All experimental data generated will be stored on computers and hardware owned by the University of Liverpool and will be directly accessible to the study's PI and research assistant for analysis and interpretation. No personal identifiers belonging to any participant will be kept at the University of Liverpool.

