6.2.2.6 Immunocytochemistry

We will use indirect immunocytochemistry (ICC) to characterise iPSC and cardiomyocyte cell lines at the protein level. This method will allow us to generate data that will confirm the simultaneous expression and cellular location of key pluripotent stem cell markers and cardiac-specific markers such as Troponin-T. The stained cells will be viewed using a fluorescence microscope and the images will be captured using a digital camera. Captured images will be interpreted and analysed with the aid of an appropriate imaging software, such as Adobe Photoshop, and data may be manipulated to include the addition of scale bars, contrast adjustment and image overlays. Data manipulation will not affect the result of the experiments in any way. Our interpretations of the data will be validated with the use of positive and negative staining controls and imaging parameters for the controls will be the same as those applied to the test dataset. In addition to obtaining data on protein expression levels, the cardiomyocyte differentiation efficiency will also be assessed by ICC. A select number of images (<5) will be captured at random and the number of cardiac TroponinT- positive cells will be divided by the total cell count. Cells will be counterstained with a nucleic acid stain (DAPI) to achieve this.

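### Sections 6.2.1 and 7.3 contradict each other on who may see clinical data, and nothing masks the laboratory operator to case/control status, so judgement-based read-outs can be made with status known

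*Protocol*

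**What the plan says.** On access to clinical data, the Protocol says two things.

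- Section 6.2.1: the participants' demographic and test data "will be recorded by the clinical team for the purposes of the study and will be accessible to the clinical team only".
- Section 7.3: clinical and demographic details that the clinical team judges relevant, without primary identifiers, "will be entered into a secure database accessible to both the clinical team and the research team". Blood tubes carry the study number, and "the research team will be able to use this number to gain relevant information from the database for data analysis purposes".

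On who does the laboratory work, section 6.2.2 says that all experimental methods "will be conducted at the University of Liverpool by the study's designated research assistant", and that the resulting data "will be directly accessible to the study's PI and research assistant for analysis and interpretation". Section 6.2.2.1 has the university's research staff allocate the cell-line codes themselves.

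On masking, the only mention of blinding is in section 7.12. It concerns stripping identifying details from data passed to project team members.

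On the read-outs, section 6.2.2.3 relies on colony picking, visual morphology and counts of observed beating areas. Section 6.2.2.6 estimates differentiation efficiency from a few fields: "A select number of images (<5) will be captured at random". Section 6.2.2.7 compares Western blot bands semi-quantitatively.

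**The concern.** The study exists to compare cells from donors with and without cardiotoxicity (section 3.1). If the person who picks colonies, counts beating areas, takes image fields and reads bands knows which donors are cases, expectation can enter the selection and the scoring, and a difference between the groups may partly reflect the observer.

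With at most 12 donors (section 3.6.1), a modest systematic shift can look like a finding. The results are meant to support funding for larger studies, so a spurious signal would be carried forward. Masking of operators and readers is a matter of study conduct that belongs in the protocol; a statistical analysis plan written later cannot supply it once the cells have been selected and scored.

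Separately, staff need to know which access rule to follow.

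**Working it through.** The protocol gives no figure on this point, so the main check sets the sections side by side.

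**1. Do 6.2.1 and 7.3 conflict?** Section 6.2.1 restricts the demographics and test results themselves: they "will be accessible to the clinical team only". Section 7.3 gives the research team access to clinical and demographic details. Leaving out primary identifiers does not reconcile them, because 6.2.1 is not limited to identifiers. The conflict stands.

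**2. Does the access in 7.3 reach the operator?** The research assistant performs the experiments and shares the analysis with the PI (6.2.2). That this person belongs to the research team is an inference, but the natural one. Because research staff assign the line codes (6.2.2.1), those codes hide nothing from them. Whether case status or LVEF is in the shared database depends on the clinical data list (Appendix 13.1.3), a separate document not at hand. I assume that group status can be learned from it, since the group comparison needs it.

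**3. Is there masking elsewhere?** None was found. Section 7.12 protects identity, and a de-identified record can still show that its donor is a case. Even if 6.2.1 prevailed, no section requires status to be withheld until measurement is complete.

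**4. Which steps are exposed?** Colony picking, morphology and beating-area counts (6.2.2.3), the choice of fewer than five image fields (6.2.2.6) and band reading (6.2.2.7). The qPCR, mass spectrometry and patch-clamp measurements are instrument-based, but they depend on which colonies and cells reached the instrument.

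**5. What could be repaired later?** Section 6.2.2.8 keeps raw electrophysiological recordings and image files, so stored material could be re-scored masked. Bias in which lines, cells or fields were taken could not be undone that way.

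**6. Illustration of size.** Assumed: no true difference, two-sided t test at alpha 0.05, an observer bias of b standard deviations between groups, and a split of 6 v 6. The protocol fixes only the maximum of 12, and Figure 1 is not shown. The test has 6 + 6 − 2 = 10 degrees of freedom and critical value 2.228. The noncentrality is b × √(n₁n₂/(n₁+n₂)) = b × √(36/12) = 1.732b. The rejection probability is P(|T| > 2.228) under the noncentral t distribution. For 4 v 8 the noncentrality is b × √(32/12) = 1.633b, with the same degrees of freedom.

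| Assumed bias b (SD) | Noncentrality, 6 v 6 | False-positive rate, 6 v 6 | False-positive rate, 4 v 8 |
|---|---|---|---|
| 0 | 0 | 5.0% | 5.0% |
| 0.25 | 0.433 | 6.8% | 6.6% |
| 0.50 | 0.866 | 12.3% | 11.5% |
| 0.75 | 1.299 | 21.8% | 19.9% |
| 1.00 | 1.732 | 34.7% | 31.5% |

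The split matters little; the assumed bias drives the result.

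**The case against.** A reader might infer that read-outs are in fact made with case status known. The protocol does not say so. Section 7.3 grants the look-up for data analysis, which section 6.2.2 treats separately from carrying out the experiments, and if 6.2.1 governs, the assistant does not see the clinical data at all. What stands is that status can be known and nothing prevents it.

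The contradiction can also be read more gently: full records for the clinical team, and a de-identified extract for the laboratory. That may be the intention, but 6.2.1 does not say it.

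Some read-outs have safeguards. Image fields are to be taken at random, control and test images share imaging parameters, image manipulation is said not to affect results, and blots use a loading control and imaging software. These help, but no method of random field selection is given and none of them masks status.

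The table could be taken as an estimate for this study. It is not one. The only t test stated between cardiotoxicity and non-cardiotoxicity samples is for the mass spectrometry data (6.2.2.7), an instrument measurement. Colony and beating-area counts serve as efficiency measures, with no case-control test stated. The bias sizes are assumed.

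It is also tempting to say that no later analysis could repair the damage. That is too absolute, since retained recordings and images allow masked re-scoring. It holds only for selection.

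**Conclusion.** The point holds in limited form. Sections 6.2.1 and 7.3 contradict each other on access to clinical data, and no section masks the research assistant to case/control status. Judgement-based steps can therefore be done with status known, which could bias the case-control comparisons. Bias in reading could be partly recovered from stored files; bias in selecting lines, cells or fields could not.

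The size is unknown. The illustrative rates (about 12% at 0.5 SD and 35% at 1 SD, against a nominal 5%) rest on assumed biases and an assumed 6 v 6 split. The conclusion also rests on two inferences: that the research assistant is part of the research team, and that the shared database reveals group status. This should be corrected, but it does not show that the results will be biased.

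**What to change.** Reconcile sections 6.2.1 and 7.3, and state the masking in section 6.2.2. Suggested wording:

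*Case/control status, LVEF and biomarker results are held by the clinical team. The laboratory works from neutral study numbers. Status, together with the de-identified clinical and biomarker data needed for the group comparisons and Aim 3, is released to the research team only after all measurements, all exclusions of lines, cells and images, and all image quantification are locked.*

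The release after lock is essential, because Aim 3 compares cell-derived biomarkers with patients' blood and with the hospital's current detection method.

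Where banked cells allow, run the assays on coded cases and controls in mixed order. This should not extend to initial blood processing: controls are identified after cases (section 3.5.1), and blood must be processed within 24 hours (section 3.6.3).

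The cost is mainly wording and database permissions; a research nurse already assigns the study numbers. The clinical team must hold the status list and handle the matching until lock. Mixed-order assays need some planning around banked stocks. Arrival order may still hint at status, so masking would be imperfect.
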